9 STUDY METHODS AND PROCEDURES

9.1 Subject Entry Procedures

9.1.1 Overview

Subjects as defined by the criteria in [Section 6.3](#) and [Section 6.4](#) will be considered for entry into this study.

9.1.2 Informed Consent

Prior to a subject's participation in the trial (i.e., changes in a subject's medical treatment and/or commencement of study related procedures), the study will be discussed with each subject. Subjects wishing to participate must provide written informed consent signing and dating an informed consent form (ICF) and other written documentation in accordance with local privacy requirements (where applicable).

9.1.3 Washout Intervals

There are no washout intervals for this study.

9.1.4 Procedures for Final Study Entry

Subjects must satisfy all inclusion and none of the exclusion criteria in order to be entered into the study.

9.1.5 Pregnancy

Females must have a negative serum pregnancy test result at Visit 1, if female of childbearing potential (those who have experienced menarche and who are not surgically sterilized [bilateral tubal ligation, hysterectomy, or bilateral oophorectomy] or post-menopausal [12 months after last menses]) and must use adequate birth control throughout the study period. Adequate birth control is defined as hormonal – oral, implantable, injectable, or transdermal contraceptives; mechanical– spermicide in conjunction with a barrier such as condom or diaphragm; IUD; or surgical sterilization of partner. For non-sexually active females, abstinence may be regarded as an adequate method of birth control.

In the event a female has a positive urine pregnancy test result at any visit following Visit 1, the Investigator will inform [REDACTED] and the sponsor about the positive pregnancy test result

within 24 hours of the time the pregnancy was reported to the Investigator, regardless of whether an AE/SAE (serious adverse event) was reported.

9.1.6 Methods for Assignment to Treatment Groups

Each subject who signs an ICF will be assigned a subject number (a five-digit number starting with the 2-digit site number followed by a sequential three-digit number assigned as xx-201). Once a subject meets all qualification criteria at Visit 2, he/she will be randomized in a 2:1 ratio via an interactive response technology system to 1 of 2 treatment groups (CSF-1 or CSF-1 vehicle), and stratified by Cohort, iris color (dark versus light [i.e., blue, green, gray, and hazel]) and by baseline manifest refraction spherical equivalent (-4.5 Diopter (D) to <-0.5 D, -0.5 D to +0.75 D, and >+0.75 D to +2.0 D).

As there is no designated study eye, the worst eye as defined by the BDCVA score at Visit 1 will be used to determine the eye for manifest refraction which is used for stratification. If both eyes have the same BDCVA score, the right eye will be selected for manifest refraction which is used for stratification. Randomization will not be stratified by site.

Randomization will be used to avoid bias in the assignment of subjects to treatment, to increase the likelihood that known and unknown subject attributes (e.g., iris color and baseline characteristics) are evenly balanced across treatment groups, and to enhance the validity of statistical comparisons across treatment groups. Double-masked treatment will be used to reduce the potential of bias during data collection and the evaluation of clinical endpoints.

This study will include approximately 170 subjects (approximately 113 randomized subjects assigned to CSF-1 and approximately 57 subjects assigned to vehicle) treated for at least 6 weeks. Any subjects treated beyond Visit 4 at the time of Protocol Amendment 2.0 approval will exit the study at the next scheduled visit ([REDACTED]).

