A sample size of 113 subjects treated with CSF-1 for at least 6 weeks will have at least 95% probability of detecting adverse events that occur at a rate of 2.66% or greater.

Safety Analysis

All safety data will be analyzed using the safety set. Safety of CSF-1 compared to vehicle will be assessed by the review of all safety parameters.

Verbatim descriptions of AEs will be mapped to Medical Dictionary for Regulatory Activities (MedDRA) terms and be presented in a data listing. A treatment-emergent adverse event (TEAE) is any event not present prior to the initiation of the drug treatment or any event already present that worsens in either intensity or frequency following exposure to the drug treatment. TEAEs will be summarized by treatment group using frequency and percent for each system organ class (SOC) and preferred term (PT) within each SOC. The number of AEs, TEAEs, serious TEAEs, and TEAEs causing premature

discontinuation will be provided by treatment group. In addition, the frequency and percentage of subjects with at least one AE, at least one TEAE, and at least one serious TEAE will also be provided by treatment group.

Similar summaries will also be presented for TEAEs related to the study drug, by severity, and by study day of onset. When reporting the incidence of AEs, a subject will only be counted once if they ever experience an event within the SOC and ever experience the individual PT within each treatment group. Number of AEs by a set interval of time will be summarized for each interval. Or number of AEs will be summarized for set intervals of time..

Changes from baseline in BDCVA, LL-BDCVA, slit lamp biomicroscopy, fluorescein staining, IOP, and dilated indirect fundus examination will be summarized descriptively at each visit where performed by treatment group.

The categorical summaries for the loss of ≥ 0.2 logMAR from baseline (yes/no) and for the loss of > 0.2 logMAR (yes/no) in BDCVA and LL-BDCVA at each visit will also be presented and compared between treatment groups using Pearson chi-squared test or Fisher's exact test if any cell counts are less than 5.

Full details of the safety analyses will be specified in the formal Statistical Analysis Plan (SAP).

Summary of Known and Potential Risks and Benefits to Human Subjects

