11 STATISTICAL HYPOTHESES AND METHODS OF ANALYSES

11.1 General Considerations

In general, quantitative/continuous data will be summarized using descriptive statistics (number of subjects [n], mean, standard deviation [SD], median, minimum, and maximum).

Qualitative/categorical data will be summarized using frequencies and percentages. Statistical testing, unless otherwise indicated, will be performed at a 2-sided 0.05 significance level.

For all variables, baseline is defined as the last measurement taken prior to the administration of the first dose of study drug. Change from baseline will be calculated as follow-up measure minus baseline measure.

Summaries and listings will be presented for all subjects, or safety set, as needed. Safety analyses will be conducted in the safety set.

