11.4 Sample Size

Approximately 170 subjects will be randomized into the study in a 2:1 ratio of CSF-1:vehicle [approximately 113 randomized subjects assigned to CSF-1 and approximately 57 subjects randomized to vehicle] completing at least 6 weeks of treatment. Any subjects treated beyond Visit 4 at the time of Protocol Amendment 2.0 approval will exit the study at the next scheduled visit. All subject data will be analyzed.

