11.6 Safety Analysis

All safety data will be analyzed using the safety set. Safety of CSF-1 compared to vehicle will be assessed by the review of all safety parameters.

Verbatim descriptions of AEs will be mapped to Medical Dictionary for Regulatory Activities (MedDRA) terms and be presented in a data listing. Treatment emergent AEs (TEAEs) is defined as any event not present prior to the initiation of the drug treatment or any event already present that worsens in either intensity or frequency following exposure to the drug treatment. TEAEs will be summarized by treatment group using frequency and percent for each system organ class (SOC) and preferred term (PT) within each SOC. The

number of AEs, TEAEs, serious TEAEs, and TEAEs causing premature discontinuation will be provided by treatment group. In addition, the frequency and percentage of subjects with at least one AE, at least one TEAE, and at least one serious TEAE will also be provided by treatment group.

Similar summaries will also be presented for TEAEs related to the study drug, by severity, and by study day of onset. When reporting the incidence of AEs, a subject will only be counted once if they ever experience an event within the SOC and ever experience the individual PT within each treatment group. The number of AEs as well as the incidence rate over the study period will also be summarized.

Changes from baseline in vital signs, BDCVA, LL-BDCVA, slit lamp biomicroscopy, IOP, and dilated indirect fundus examination and endothelial cell density will be summarized descriptively for at each visit by treatment group. Changes from baseline in endothelial cell density parameters will be tested between treatment groups using two-sample t-tests.

The categorical summaries for the loss of ≥ 0.2 logMAR from baseline (yes/no) and for the loss of > 0.2 logMAR (yes/no) in BDCVA and LL-BDCVA at each visit will also be presented and compared between treatment groups using Pearson chi-squared test or Fisher's exact test if any cell counts are less than 5.

Full details of the safety analyses will be specified in the formal Statistical Analysis Plan.

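### The named between-group tests ignore the factors that stratify randomisation; they stay valid, but lose some power to show harm if those factors are prognostic

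*Combined protocol and SAP*

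**What the plan says.** Section 9.1.6 randomises 2:1, "stratified by Cohort, iris color (dark versus light [i.e., blue, green, gray, and hazel" being light), and further "by baseline manifest refraction spherical equivalent (-4.5 Diopter (D) to <-0.5 D, -0.5 D to +0.75 D, and >+0.75 D to +2.0 D"). Site is not a factor. The legible text does not define the levels of Cohort; redaction may explain that.

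Section 11.6 names two between-group tests. Losses of at least 0.2 and of more than 0.2 logMAR in BDCVA and LL-BDCVA are "compared between treatment groups using Pearson chi-squared test", replaced by Fisher's exact test when any cell count is below 5. The synopsis repeats this. For the cornea: "Changes from baseline in endothelial cell density parameters will be tested between treatment groups using two-sample t-tests". Section 11.1 sets the level: "Statistical testing, unless otherwise indicated, will be performed at a 2-sided 0.05 significance level".

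No legible section brings the stratification factors into either test or gives a reason for leaving them out. Both the synopsis and Section 11.6 leave full details to a formal SAP, and the documents contain no separate SAP text.

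**The concern.** Stratified allocation holds the arms nearly balanced within each stratum, so differences between strata contribute little to the arm comparison. An unstratified test still counts those differences in its standard error. When the strata predict the outcome, the standard error is too large, the test rejects less often than 5% under no effect, and it is less likely to show a real difference.

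The only objective (Section 4.1) is safety against vehicle. A test that leans towards no difference errs in the less protective direction there.

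**Working it through.** **1. The plan's own figure.** The synopsis bases the sample size on 113 CSF-1 subjects and states that this number "will have at least 95% probability of detecting adverse events that occur at a rate of 2.66% or greater". The chance of at least one event is 1 − (1 − 0.0266)^113 = 95.25%. The exact threshold is 1 − 0.05^(1/113) = 2.62%, and the rule of three gives 3/113 = 2.65%. Section 11.4 has "Approximately 170 subjects will be randomized into the study in a 2:1 ratio of CSF-1:vehicle": 170 × 2/3 = 113.3 and 170/3 = 56.7. Both figures reproduce. Neither depends on a between-group test, so this point does not touch them.

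**2. Continuous test.** Let R² be the share of outcome variance explained by the strata (an assumption). The unadjusted standard error is too large by the factor 1/√(1 − R²): 1.026 at 0.05, 1.054 at 0.10 and 1.118 at 0.20.

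Simulation: 170 subjects, permuted blocks of 3 within 12 strata (assuming two Cohort levels), 4,000 trials per setting, effect 0.455 SD (80% unadjusted power).

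| R² | t-test type I error | t-test power | Adjusted power | Gain (points) |
|---|---|---|---|---|
| 0 | 5.0% | 80.4% | 80.6% | 0.2 |
| 0.05 | 4.5% | 80.0% | 81.5% | 1.5 |
| 0.10 | 3.5% | 80.2% | 82.7% | 2.5 |
| 0.20 | 3.0% | 82.3% | 87.9% | 5.6 |

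The adjusted model held its type I error at 4.6–5.4%. Simulation error is about ±0.7 points for type I error and ±1.2 for power.

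**3. Binary test.** Two effects must be kept apart: ignoring the strata, and switching to Fisher's test. Three tests are therefore compared: the stated rule, a plain unstratified chi-squared test, and CMH.

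Assumptions: 113:57 over six iris-by-MRSE strata of 28 or 29, vehicle rates evenly spaced on the log scale, a common odds ratio, one outcome per subject.

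| Vehicle rates across strata | Odds ratio | Stated rule | Unstratified chi-squared | CMH | Due to Fisher (points) | Due to strata (points) |
|---|---|---|---|---|---|---|
| 4.5% in all | 4 | 54% | 63% | 62% | 9 | −1 |
| 5–15% | 3 | 60% | 61% | 63% | 1 | 2 |
| 1–12% | 4 | 47% | 55% | 61% | 8 | 6 |
| 1–40% | 3 | 44% | 45% | 62% | 1 | 17 |

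A 3–6% spread at odds ratio 4 gave 55.9% against 58.9%, a gain of 3 points from stratifying.

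**4. Sensitivity of the steep rows.** They depend on how 2:1 is rounded within small strata. In a 20,000-replicate check, ten vehicle subjects in each of the three highest-rate strata and nine in the others gave 56.3% to 62.4% (1–12%) and 43.9% to 62.4% (1–40%). Spreading the tens over low- and high-rate strata gave 59.6% to 60.7% and 51.9% to 60.9%, gains of only 1 and 9 points. So 6–17 lies towards the upper end.

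**5. Twelve strata.** With Cohort included (two levels assumed), CMH against unstratified chi-squared differed by −0.4 to +1.6 points when the odds ratio per SD of the stratum score was 1–2, and by +3.0 to +4.0 at 3.

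**The case against.** **The loss is conditional.** A reader might infer that power is certainly lost. The documents give no figure for how well iris color, MRSE or Cohort predicts any safety outcome, and with no stratum effect the cost is nil. This objection stands.

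**Fisher's test explains much of the apparent gain.** A reader might attribute the whole gap between the stated rule and CMH to ignored strata. With equal rates in every stratum the gap is 8 points (54% against 62%), and stratification contributes none of it. Likewise, in a run with equal rates the stated rule's type I error was 3.0% and unstratified chi-squared's 4.1%, so a sub-nominal level alone does not show that strata matter. This stands too.

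**False positives are not inflated.** Only the standard error is overstated; the tests remain valid.

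**The study is largely descriptive.** Its size rests on seeing at least one event in the CSF-1 arm, and no between-group test has a stated power. This limits the weight of the point, but the protocol still names these tests and will report their p-values.

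**Endothelial cell density may not be measured.** It is tested in Section 11.6 but absent from Sections 7.1 and 11.3 and from the synopsis. The visit procedures are redacted. That must be settled first.

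**An SAP could add stratified analyses.** It could, but an SAP that follows the tests named in Section 11.6 would carry the gap forward.

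**Conclusion.** The mismatch between Sections 9.1.6 and 11.6 is real and its direction is clear: if the factors are prognostic, the named tests are conservative and lose some power to show harm; if not, nothing is lost.

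The gain from stratifying the binary test, apart from the Fisher switch, is about 0–3 points under mild gradients. Under steep 10- to 40-fold gradients it is about 6–17 points in the main runs, and less under other stratum sizes. For the t-test it is about 1.5–6 points at R² of 0.05–0.20. These figures rest on assumed rates, effects and stratum sizes, on two assumed Cohort levels where Cohort is included, and on subject-level outcomes.

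The documents do not support reading this as an invalid test or a wrong sample size. No stated figure is wrong. It is a free improvement in analysis.

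**What to change.** In Section 11.6 and the synopsis, compare the acuity-loss proportions with a CMH test stratified by the randomisation factors. State in advance how sparse strata are pooled: 12 strata would hold about 170/12 ≈ 14 subjects each. Use an exact stratified version when events are very few, accepting that it gives back part of the power gain. Define Cohort where that can be disclosed.

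Confirm whether endothelial cell density is measured. If it is, analyse its change with a linear model containing the randomisation factors and the baseline value; if not, remove the test.

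If the unadjusted tests are kept, state the reason.

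The cost is wording and a few lines of code, with no new data or subjects. The small downside is that strata with only one arm or no events contribute nothing to the CMH test.

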9.2 Concurrent Therapies and Medical History

The use of any concurrent medication, prescription, or over-the-counter (OTC) medication taken within 30 days of Visit 1, is to be recorded on the subject's source document and corresponding electronic case report form (eCRF) along with the reason the medication was taken.

All significant current and relevant ocular and non-ocular medical and surgical history is to be recorded on the subject's source document and corresponding eCRF. Any significant general and surgical health history should be recorded on the subject's source documents.

Concurrent enrollment in another investigational drug or medical device study is not permitted.

9.2.1 Prohibited Medications/Treatments

Soft contact lenses must be removed at least 7 days prior to study Visit 1 and during the study, and RGP contact lenses must be removed at least 14 days prior to study Visit 1 and during the study.

Also, the following medications are prohibited during the timeframe noted below:

- a. The day of the study visit or within 12 hours prior to a study visit (chronic, daily

use is not allowed):

- i. nonsteroidal anti-inflammatory drugs (NSAIDs) (e.g., Advil®, Motrin®) except for once daily Aspirin used in (cardiovascular) prophylactic dose of 81 mg. Topical NSAIDs are allowed.
- ii. narcotic (opiate class) pain medication (e.g., codeine, OxyContin®, Vicodin®, Tramadol®)

b. Two (2) weeks (14 days) prior to Visit 1 or for the duration of the study:

- i. bladder medications [cholinergics (e.g., Urecholine®, bethanechol), anticholinergics (e.g., oxybutynin) and antimuscarinics (e.g., fesoterodine)]
- ii. attention-deficit/hyperactivity disorder (ADHD) medications
- iii. Latisse®, Upneeq®, Vuity®, and Lumify®

c. During the year preceding the enrollment in the study and during the entire duration of the study:

[figure not shown]
- i. Any antipsychotics
- ii. Any antidepressants

9.3 Examination Procedures

9.3.1 Procedures to be performed at the Study Visit with Regard to Study Objective

The following procedures should be conducted at each study visit **in the following order**:

9.3.1.1 Visit 1 (Day -30 to Day -7): Screening

9.3.1.2 Visit 2 (Week 1/Day 1): Baseline Assessments

[REDACTED]

9.3.1.3 Visit 3 (Week 2/Day 15 ± 2 days): Safety Assessments

[REDACTED]

9.3.1.4 Visit 4 (Week 6 + 7 days): Safety Assessments & Exit Visit (for all subjects who have not completed Visit 4 at the time of Protocol Amendment 2.0 approval)

[REDACTED]

9.3.1.5 Visit 5 (Week 12 ± 7 days): Safety Assessments & Exit Visit (for all subjects who have completed Visit 4 at the time of Protocol Amendment 2.0 approval)

A horizontal bar chart illustrating the percentage of respondents who have heard of various topics. The y-axis lists the topics, and the x-axis represents the percentage from 0% to 100%. The bars are black and set against a white background.

Topic	Percentage
Healthcare	98%
Technology	95%
Finance	92%
Politics	88%
Entertainment	85%
Science	82%
Food	78%
Sports	75%
Business	72%
Art	68%
History	65%
Geography	62%
Mathematics	58%
Chemistry	55%
Physics	52%
Biology	48%
Spanish	45%
French	42%
German	38%
Japanese	35%
Korean	32%
Chinese	28%
Arabic	25%
Russian	22%
Swahili	18%
Portuguese	15%
Urdu	12%
Hindi	10%
Malay	8%
Turkish	6%
Polish	4%
Swedish	3%
French Canadian	2%
Welsh	1%
Welsh Canadian	1%

9.3.1.6 Visit 6 (Week 18 ± 7 days): Safety Assessments & Exit Visit (for all subjects who have completed Visit 5 at the time of Protocol Amendment 2.0 approval)

A horizontal bar chart illustrating the distribution of 15000 samples across 15 categories. The categories are represented by black horizontal bars of varying lengths. The x-axis is labeled 'Category' and the y-axis is labeled 'Count'.

Category	Count
1	10000
2	10000
3	10000
4	10000
5	10000
6	10000
7	10000
8	10000
9	10000
10	10000
11	10000
12	10000
13	10000
14	10000
15	10000

9.3.1.7 Visit 7 (Week 21 ± 7 days): Safety Assessments & Exit Visit (for all subjects who have completed Visit 6 at the time of Protocol Amendment 2.0 approval)

9.4 Schedule of Visits, Measurements and Dosing

9.4.1 Scheduled Visit

Refer to [REDACTED] for a schedule of measurements at each visit.

9.4.2 Unscheduled Visits

In the case of an AE, an unscheduled visit may occur. The investigator may perform additional assessments at their discretion. All additional assessments will be documented in the subject's source document.

9.5 Compliance with Protocol

This study will be conducted in compliance with the protocol, the ethical principles that have their origin in the Declaration of Helsinki, the International Council for Harmonisation (ICH) consolidated Guideline E6 for Good Clinical Practice (GCP) (CPMP/ICH/135/95), and applicable regulatory requirement(s), such as Food and Drug Administration (FDA) GCP Regulations and Code of Federal Regulations (CFR) Title 21, parts 11, 50, 54, 56 and 312, as appropriate.

9.6 Subject Disposition

9.6.1 Completed Subjects

A completed subject is one who has not been discontinued from the study.

9.6.2 Withdrawn Subjects

A subject may be withdrawn for meeting any of the withdrawal criteria as described in [Section 6.5](#).

9.6.3 Discontinued Subjects

A discontinued subject is one who does not complete the protocol-defined study visits. A subject may be discontinued at the discretion of the investigator, sponsor, and/or the institutional review board (IRB). Notification of early discontinuation from the study and the reason for discontinuation will be made to the sponsor and/or [REDACTED].

Prior to discontinuing a subject, every effort should be made to obtain as much follow-up data as possible, and to retrieve all study materials. AEs will be followed as described in [Section 10.0](#).

9.7 Study Termination

The study may be terminated at any time by the investigator, the sponsor, and/or [REDACTED] with appropriate notification.

9.8 Study Duration

This study is comprised of up to 4 visits over a total duration of approximately 6 weeks. All subjects treated beyond Visit 4 at the time of Protocol Amendment 2.0 approval will exit the study at the next scheduled visit ([REDACTED]).

9.9 Monitoring and Data Quality Assurance

During the course of the study a qualified study monitor will make routine site visits to review protocol compliance, assess IP accountability, and ensure the study is being conducted according to the pertinent regulatory requirements.

Prior to the start of the study, investigator and study site personnel are trained on protocol, CRFs, regulatory obligations and other relevant materials to conduct the study. The study monitor will determine compliance and take corrective action when necessary. Details of the study monitoring are outlined in a monitoring plan.

